### **7.4 Quality of life and/or Outcomes**

Psychosocial assessments will be provided to the subjects by a trained and fully bilingual clinical coordinator/research nurse with experience in conducting psychosocial assessments in prostate cancer populations. Subjects can fill in the assessments on their own, if they need help answering or understanding the questions a nurse\coordinator will be available. We will make every effort to pair our psychosocial assessment visits with scheduled clinic appointments to reduce participant burden. The psychosocial battery will last between 30-40 minutes. All assessments will be conducted in private rooms in our clinics. All psychosocial data will be de-identified and only coded by participant number. Should a participant display any significant signs of distress (e.g., high levels of anxiety, depressed mood or spontaneous comments suggesting a need for psychosocial care), we will refer participants to appropriate psychosocial resources within our medical center.

## **8. ADVERSE EVENT REPORTING**

In this therapeutic trial, all patients will undergo the standard of care for men undergoing radical prostatectomy. The only difference is the implantation of amniotic membrane in men who are allocated to the implantation arm. The only adverse event that could be anticipated from Membrane Implantation is infection, but there is no data to suggest an increased risk of this. Adverse effects from RARP include bleeding, infection, urinary incontinence and impotence but these are all well known to be associated with surgery. Secondly, surgery is not the intervention being assessed in this trial and therefore we will stick to reporting on adverse events that are more likely to be related to the graft itself. Regardless, all serious adverse events will be captured. In the unlikely event that a study patient experiences an adverse reaction to a study related procedure, this will be reported to the University of Miami Institutional Review Board as per their policies and using the grading scales of the NIH CTCAE version 4.0

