## 9. DATA AND SAFETY MONITORING PLAN

The study investigators will report to the Sylvester Comprehensive Cancer Center Data and Safety Monitoring Committee (DSMC) to ensure data quality and subject safety. The investigators will conduct continuous reviews of the data and subject safety, keeping track of the number of subjects, significant toxicities in accordance with the protocol and observed responses, which will be discussed at DSMC committee meetings. All grade 3-5 adverse events, regardless of association with the membrane implantation, will be entered into Velos and reviewed at DMSC meetings. In addition, all adverse reactions considered "serious" will be entered into Velos and reviewed by the DSMC on an ongoing basis. If a death occurs within 30 days of radical prostatectomy and membrane implantation and is determined to be related to the study, the investigators will notify the DSMC chair within 1 business day. If an increase in the frequency of grade 3 or 4 adverse events is noted in the study, a report will be submitted to the DSMC at the time the increased rate is identified. If at any time the principal investigator stops enrollment or stops the study due to safety issues, the DSMC chair and manager will be notified within 1 business day and a formal letter will be sent to the DSMC to be received within 10 business days.

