## 10.6 Statistical Analysis

The difference in the SHIM score decline in each group from baseline to 12 months post RARP with 95% CIs will be reported as the primary endpoint for the study. Linear regression models will be fitted to determine the likely decline in SHIM scores based on receipt of a membrane during RARP. These models will control for baseline SHIM scores, age, and a binary indicator of the use of any oral erectile aids, in addition to other important demographic and clinic factors.

Among men with a SHIM greater than or equal to 17, the proportion of men in each group with a SHIM of 17 or greater, able to achieve an erection sufficient for intercourse more than 50% of the time, or not requiring any invasive erectile aids at each follow up interval will be reported and compared using counts and percentages with 95% CLs. Logistic regression models will be fitted to determine the likelihood of having achieving each result controlling for age and a binary indicator of the use of any oral erectile aids, in addition to other important demographic and clinic factors. Both unadjusted and adjusted odds ratios with 95% CIs and their corresponding p-values will be reported

In addition, we will report by treatment group adverse event rates by grade and attribution, and the number and percentage of men not needing pads.

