## 10.7 Interim Monitoring

### 10.7.1 Role of the Research Team and the DSMC

The Research Team will continuously monitor study accruals and adverse events from both treatment arms. Patients will be monitored closely **during treatment and subsequently over 30 days** for any **adverse event** potentially related to treatment. All toxicities, regardless their grade, will be recorded in the patient case report form using NCI/CTEP Common Terminology Criteria for Adverse Events (CTCAE) version 4.03. In addition, a one interim analysis **of the primary efficacy endpoint** is planned in first 50% of study patients.

The Sylvester Comprehensive Cancer Center's Data and Safety Monitoring Committee (DSMC) will monitor this protocol according to the Cancer Center's DSM Plan. In its oversight capacity, the DSMC bears responsibility for suspending or terminating this study.

DSMC oversight of the conduct of this trial includes ongoing review of accrual, adverse event data, and interim analysis of response to treatment. The guidelines appearing in Sections 10.7.2, and 10.7.3 are offered for DSMC consideration in assessing accrual, adverse events, and response to treatment. In addition, the DSMC will review reports from all audits, site visits, or study reviews pertaining to this clinical trial and take appropriate action.

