#### **11.5 Recording and Processing of Data**

Data for this study will be entered into electronic CRFs in RedCap. A CRF is required for every patient who received any study intervention. The investigator will ensure that the CRF's are accurate, complete, legible and timely. Separate source records are required to support all CRF entries. All corrections to study data will be made by drawing a single line through the information to be corrected without obscuring it. All corrections will be initialed, dated and explained, if necessary. **Do not use “white-out” or obscuring correction tape.**

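### Section 8 limits non-serious adverse event reporting to events thought related to the graft, in conflict with Sections 7.3, 9 and 10.7.1; if it governs collection, the two arms may not be ascertained alike

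*Combined protocol and SAP*

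**What the plan says.** Five parts of the combined protocol and SAP set the scope of adverse event capture, and they differ.

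- **Section 8** argues that surgery is not what the trial tests, and concludes: "therefore we will stick to reporting on adverse events that are more likely to be related to the graft itself". The next sentence makes an exception: "Regardless, all serious adverse events will be captured". The section also states that "The only adverse event that could be anticipated from Membrane Implantation is infection", and that "Adverse effects from RARP include bleeding, infection, urinary incontinence and impotence".
- **Section 7.3** says that every adverse event will still be reported, and refers the reader to Section 8 for how.
- **Section 9** says: "All grade 3-5 adverse events, regardless of association with the membrane implantation, will be entered into Velos". It adds reactions considered serious. It does not mention grade 1-2 events.
- **Section 10.7.1** monitors adverse events in both arms during treatment and for 30 days afterwards, and says: "All toxicities, regardless their grade, will be recorded in the patient case report form".
- **Section 11.5** says: "A CRF is required for every patient who received any study intervention". Section 1.2 describes the study intervention as membrane placement.

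On the analysis side, Section 10.3 lists adverse event rates classified by type, grade and relationship to treatment. Section 10.6 says "we will report by treatment group adverse event rates by grade and attribution". Section 10.7.2 applies a guideline based on treatment-related events to each arm separately, control included.

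**The concern.** Section 8 makes the judged link to the graft a condition for reporting a non-serious event. Only Arm I men receive a graft, so a filter of this kind need not act equally on the two arms. Infection shows the problem: it is the one event the protocol anticipates from the membrane, and it is also a listed effect of the operation that both arms undergo. Attribution in a single patient cannot reliably separate the two sources. A randomised comparison can, but only if infections are counted the same way in both arms.

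At stake is the safety output in Sections 10.3 and 10.6. If Section 8 decides what is collected, the non-serious part of that output could show a membrane-arm excess that is not there, or could miss events in both arms. Staff following different sections would also produce a table whose contents depend on which section they followed.

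**Working it through.** The documents state no figure for this point, so the main check sets the rules side by side.

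| Event | Section 8 | Section 9 | Section 10.7.1 |
|---|---|---|---|
| Serious, either arm | captured | captured | recorded |
| Non-serious, grade 3 or above, judged graft-related | reported | captured | recorded |
| Non-serious, grade 3 or above, not judged graft-related | not reported | captured | recorded |
| Non-serious, grade 1-2, judged graft-related | reported | not required | recorded |
| Non-serious, grade 1-2, not judged graft-related | not reported | not required | recorded |

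Three things follow.

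1. Section 8 contradicts Section 9 in the third row and Section 10.7.1 in the third and fifth rows. It also fails to deliver what Section 7.3 says it contains.
2. Serious events are captured under every section, so they carry no asymmetry.
3. If Section 9 is followed alongside Section 8, the gap shrinks to non-serious grade 1-2 events.

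**Two readings of the Section 8 filter.** Read as causal attribution, a control man cannot satisfy it, while the same non-serious infection in a membrane man may. Read by event type, infection would be reported in both arms, and the loss would be non-serious events of other types, in both arms.

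**Illustration of the causal reading.** Inputs: n = 70 per arm (Section 4.1); p, the true rate of a non-serious event, equal in both arms; q, the share of membrane-arm cases judged graft-related. Both p and q are assumptions, because the documents give neither.

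- Expected membrane-arm reports = n × p × q
- Expected control reports = 0
- Apparent difference = p × q, when the true difference is 0

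With q = 0.5:

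- p = 5%: 70 × 0.05 × 0.5 = 1.75 against 0 (2.5 percentage points)
- p = 10%: 70 × 0.10 × 0.5 = 3.5 against 0 (5 points)
- p = 20%: 70 × 0.20 × 0.5 = 7 against 0 (10 points)

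Over a wider grid the count runs from 70 × 0.05 × 0.25 = 0.875 (p = 5%, q = 25%) to 70 × 0.30 × 1 = 21 (p = 30%, q = 100%), again against 0.

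Under Section 10.7.1, with every event recorded in both arms, the expected counts are equal: 3.5 and 3.5 at p = 5%, 7 and 7 at 10%, 14 and 14 at 20%. The apparent difference is then zero.

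**The case against.** The strongest reply is that Section 8 does not control the analysis. Sections 10.3 and 10.6 use attribution to classify events, not to admit them. Section 10.7.1 covers both arms and all grades, and Section 7.3 shows that broad capture was intended. One could add that Section 8 speaks of reporting and Section 10.7.1 of recording, so that everything is recorded and only some of it reported. This stands in part: the distortion arises only if Section 8 decides what reaches the dataset or the table. It does not remove the conflict, because Section 7.3 sends the reader to Section 8 for the rule and nothing says which section prevails.

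A second reply is that the filter may concern event types, so that infection counts in both arms. The text allows this. Section 8's reasoning, that surgical effects are known and surgery is not under test, leans towards dropping a control man's non-serious infection, but it does not settle the matter. The event-type reading replaces asymmetry with incomplete ascertainment.

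Some stronger inferences are tempting, and the documents do not support them:

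- **That the whole by-arm safety comparison is necessarily biased.** Serious events are exempt, Section 9 protects grade 3-5 events if followed, and the rest depends on how Section 8 is read and used.
- **That Section 9 records all events.** It covers grade 3-5 and serious events only.
- **That control men will have no case report form.** The literal wording of Section 11.5 invites this, but Section 10.7.1 puts toxicities in the form while monitoring both arms, and Section 7.2 uses the word intervention loosely for assessments that apply to all men. It is a wording slip worth tidying.
- **That attribution is judged by people who know the arm.** Section 4.3 shows that coordinators and the requesting team member learn it, but no section says who assigns attribution.
- **That attribution has no meaning in the control arm.** The planned variable is relationship to treatment, and Section 10.7.2 uses treatment-related events in each arm.

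**Conclusion.** The point holds as an internal inconsistency with a conditional consequence. For non-serious events, the scope in Section 8 cannot be reconciled with Sections 7.3, 9 (grade 3 and above) and 10.7.1. If Section 8 governs collection and means causal attribution, capture is asymmetric and the rates in Sections 10.3 and 10.6 could show a false membrane-arm excess. If it means event type, both arms are under-ascertained.

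The size cannot be derived from the documents. The illustrative gap of about 2-7 of 70 against 0 of 70 rests on three assumptions: equal true rates of 5-20%, half of membrane-arm cases attributed to the graft, and strict use of the causal reading. Section 10.6 plans to report adverse events by arm and names no test for them, so what is at risk is a misleading descriptive table. The primary endpoint is not touched. The change should be made, because infection can be attributed to the membrane or to the surgery only by counting it equally in both arms.

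**What to change.** - **Section 8:** delete the restriction to graft-related events. State that all adverse events of any grade are recorded in both arms, over the same window from surgery, with attribution recorded as a variable and not used as a condition for inclusion.
- **Section 7.3:** align the cross-reference, so that Section 8 contains what it is said to contain.
- **Section 10.6:** make by-arm rates regardless of attribution the main safety table, with infection shown as its own line. Keep the attribution breakdown as a secondary table in both arms, since Section 10.7.2 needs treatment-related events in each.
- **Section 11.5:** require a case report form for every randomised man.

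The cost is an amendment of wording in four sections. No data are needed beyond those Section 10.7.1 already requires.

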## 9. DATA AND SAFETY MONITORING PLAN

The study investigators will report to the Sylvester Comprehensive Cancer Center Data and Safety Monitoring Committee (DSMC) to ensure data quality and subject safety. The investigators will conduct continuous reviews of the data and subject safety, keeping track of the number of subjects, significant toxicities in accordance with the protocol and observed responses, which will be discussed at DSMC committee meetings. All grade 3-5 adverse events, regardless of association with the membrane implantation, will be entered into Velos and reviewed at DMSC meetings. In addition, all adverse reactions considered "serious" will be entered into Velos and reviewed by the DSMC on an ongoing basis. If a death occurs within 30 days of radical prostatectomy and membrane implantation and is determined to be related to the study, the investigators will notify the DSMC chair within 1 business day. If an increase in the frequency of grade 3 or 4 adverse events is noted in the study, a report will be submitted to the DSMC at the time the increased rate is identified. If at any time the principal investigator stops enrollment or stops the study due to safety issues, the DSMC chair and manager will be notified within 1 business day and a formal letter will be sent to the DSMC to be received within 10 business days.

## 10. STATISTICAL CONSIDERATIONS

This is a blinded two-arm randomized phase 2 trial. Patients will be randomized in a ratio 1:1 to study arms, the experimental Arm I (membrane placement) and control Arm II (no membrane placement, standard of care surgery), using a permuted block design stratified by baseline SHIM score (<17 vs. >=17), and use of ANY erectile aids (Yes vs. No) in the last 3 months.

All analyses will be performed as an intention to treat and as per Protocol. Although there is no data to suggest an increased risk of any potential adverse effects with placement of a sling, we will monitor adverse events as per section 10.7.2. An interim analysis of the primary efficacy endpoint, change in SHIM score, will be performed as part of the analysis plan as described in section 10.7.3..

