## 1.4 Preliminary Studies

Patel et al conducted an interventional trial wherein men with prostate cancer undergoing Robot Assisted Radical Prostatectomy (RARP) were implanted with a dehydrated human amnion chorion allograft (dHACM) around the neuro-vascular bundle. The subjects were previously continent (American Urological Association Symptom Score <10) as well as potent (Sexual History Inventory for Men Score >19).

This study showed that dHACM placement significantly facilitated early return to potency and continence. Continence at 8 week returned in 81.0% of the dHACM group and 74.1% of the no-dHACM group ( $p = 0.373$ ). Mean time to continence was enhanced in dHACM patients (1.21 months) versus no-dHACM patients (1.83 months;  $p = 0.033$ ). Potency at 8 weeks returned in 65.5% of the dHACM patients and 51.7% of the no-dHACM group ( $p = 0.132$ ). Mean time to potency was enhanced in dHACM group, (1.34 months), compared to no-dHACM (3.39 months;  $p = 0.007$ ). Graft placement enhanced mean time to continence and potency

As a result of this study many centers have begun using amnionic membranes with the hope that they will induce an earlier recovery of potency and urinary control. Furthermore, many patients have been requesting to have amniotic membranes placed at the time of surgery for similar beliefs regarding it's potential utility for functional recovery. However, a major limitation of this study is that it was conducted as an observational study with a computer matched cohort rather than a randomized trial, leaving a significant potential for bias. As a result, the findings should be considered hypothesis generating at best and further validation should be required in randomized studies before this technique can be considered in contemporary clinical practice.

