## 4. STUDY DESIGN

This is a phase 2 prospective randomized trial investigating the impact of amniotic membrane placement over the neurovascular bundles after bilateral nerve sparing robot assisted radical prostatectomy on potency. The study will have a control arm that will follow standard of care surgery, without placement of any membranes.

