#### **4.3 Study Randomization**

Randomization of study patients will be done in equal proportion to Arm I (membrane placement) and Arm II (no membrane placement, standard of care surgery) using a permuted block design stratified by baseline SHIM score (<17 vs.  $\geq 17$ ), and use of **ANY** erectile aids (Yes vs. No) in the last 3 months.

Randomization lists for each stratum will be prepared by SCCC Biostatistics prior to the first patient enrollment and provided to the SCCC CRS-Informatics office where they will be programmed and customized as per randomization requirement using the CIERRA system. Members of the study team, including those responsible for patient enrollment, will not have access to the randomization lists.

After each patient's study eligibility is confirmed and the informed consent is signed, CRS coordinators will enter the required patient information into the CIERRA system in order to register the patient. The CRS coordinators will receive the designated patient ID, study arm, randomization number, and randomization date. CRS coordinators will print the randomization confirmation form from the CIERRA system and place it in the patient's research chart and then notify the requesting member of the study team of the treatment assignment for the new randomized patient.

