#### **4.4 Follow Up and Analyses**

Patients will be followed up every three months ( $\pm$  1 month) for a total of one year. This follow up schedule meets the current standard of care after radical prostatectomy. At each follow up a serum PSA will be assessed for recurrence on prostate cancer. To investigate primary and secondary endpoints a self-reported validated questionnaire will be provided assessing measures of potency. Finally, the use of pads for urinary leakage will be

assessed at each time point. After the first year, there will be annual follow up with PSA measurements and an assessment of any secondary therapies for 5 years. Further details regarding the primary and secondary endpoints can be found in Section 3. The analyses will be performed as an intention to treat analysis. More details regarding the analyses of primary and secondary endpoints can be found in Section 10.

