## 5. STUDY ENTRY AND ENROLLMENT AND WITHDRAWAL

### 5.1 Nerve sparing robotic assisted radical prostatectomy

In the USA, enthusiasm for the robotic- assisted technique currently overshadows conventional laparoscopic radical prostatectomy. Two series in the US have demonstrated the successful transfer from the open to laparoscopic technique by aid of the robotic device. Similar functional and oncological outcome have been noted between open and robotic prostatectomy,. However, the robotic approach has the advantage of faster recovery and less blood loss. As a result the majority of the University of Miami cases are done robotically.

The operative procedure for nerve sparing RARP has the following steps:

- Incision is done on the peritoneum overlying the vas deferens and seminal vesicle.
- Seminal vesicle and the vas deferens are dissected out bilaterally.
- The plane below the prostate and above the rectum is developed towards the apex of the prostate.
- Anterior dissection (dropping) of the bladder is performed and the endo-pelvic fascia is opened bilaterally.
- Junction of the prostate and bladder is identified.
- Incision is taken at the bladder neck both anteriorly and posteriorly.
- The neuro-vascular bundle is identified and dissected from the prostatic pedicle.
- Prostatic pedicle will be ligated and cut with the use of hemo clips.
- Then the apical dissection will be conducted by dividing the dorsal venous complex and urethra
- A *vesico-urethral anastomosis* will be conducted and will be checked for no leakage.
- If indicated a bilateral pelvic lymph node dissection may be performed.

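### Section 10 calls the trial blinded without saying who is blinded, how or until when, and Section 4.3 does not hold the arm back until the nerve bundles are dissected

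*Combined protocol and SAP*

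**What the plan says.** The word blinded appears once, in the first sentence of Section 10: "This is a blinded two-arm randomized phase 2 trial". Section 4 describes the same design without it: "This is a phase 2 prospective randomized trial investigating the impact of amniotic membrane placement over the neurovascular bundles". The control arm there is standard surgery with no membrane, and no sham is described.

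Section 4.3 contains one protective sentence: "Members of the study team, including those responsible for patient enrollment, will not have access to the randomization lists". The same section then sets out what happens once eligibility is confirmed and consent signed. First, "CRS coordinators will receive the designated patient ID, study arm, randomization number, and randomization date". The coordinators next print the confirmation form, file it in the research chart, and "notify the requesting member of the study team of the treatment assignment for the new randomized patient". No timing relative to the operation is given, and no limit is set on who may be told next.

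Section 5.1 lists the operative steps, including this one: "The neuro-vascular bundle is identified and dissected from the prostatic pedicle". Section 5.2 places the membrane after the prostate has been removed and before the anastomosis.

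On outcome collection, Section 4.4 says: "To investigate primary and secondary endpoints a self-reported validated questionnaire will be provided assessing measures of potency". Section 7.4 lets men complete the forms alone or with help from a nurse or coordinator, and does not say whether the helper may know the arm.

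**The concern.** Keeping the lists from the team protects the assignment before it is made. It does not blind anyone afterwards, and the steps that follow in Section 4.3 are disclosure steps. Two stages of this trial are sensitive to knowing the arm.

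- **Nerve dissection.** It is done by hand and comes before the membrane. A surgeon who knew the arm could, without intending it, dissect differently.
- **The 12-month SHIM.** The patient is the assessor. Section 1.4 reports that "many patients have been requesting to have amniotic membranes placed at the time of surgery for similar beliefs". That describes patients in general rather than those enrolled, but it makes expectation effects plausible.

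Section 1.4 criticises the earlier matched-cohort study for its potential for bias, and this trial is meant to answer that criticism. As the plan stands, its report could claim a blinded comparison that the protocol neither defines nor protects.

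**Working it through.** **Step 1: the text, role by role.**

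| Role | What the plan says about knowing the arm |
|---|---|
| Enrolling staff, before assignment | No access to the lists (4.3) |
| Coordinators | Receive the arm after eligibility and consent (4.3) |
| Requesting team member | Notified of the arm (4.3); may or may not be the surgeon |
| Surgeon | Must know at membrane placement (5.2); nothing on earlier knowledge |
| Patient | Nothing stated |
| Questionnaire helper | Nothing stated (7.4) |

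**Step 2: when the arm is needed.** Bundle dissection is one of the steps that free the prostate (5.1). Placement follows removal (5.2). The arm is therefore not needed until dissection is finished, and no step in 4.3 makes use of that interval.

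**Step 3: what a bias could do (illustration only).** No figure in the plan is disputed on this point, and the plan gives no size for any bias, so the shifts below are assumptions.

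Inputs: 70 per arm (4.1); SD of change 8.5 observed and 9.8 upper limit (10.5); one interim look at about 35 per arm, with nominal two-sided levels 0.003 and 0.049 (10.7.3), that is z = 2.968 and 1.969.

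For a between-arm shift b:

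- SE = SD × √(2/70), which is 8.5 × 0.1690 = 1.437 or 9.8 × 0.1690 = 1.657.
- Mean of the final statistic = b/SE; mean of the interim statistic = (b/SE) × √0.5; correlation = √0.5 = 0.707.
- P(reject) = 1 − P(|Z1| < 2.968 and |Z2| < 1.969), from the bivariate normal.

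Check against the plan's own figures: b = 0 returns 0.050, the stated total alpha. The first row of Table 10.1 (difference 3.80, SD 8) has SE = 8 × 0.1690 = 1.352 and means 2.810 (final) and 1.987 (interim), and returns 0.801 against the stated 0.80.

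With no true effect and the same shift at both looks:

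| Assumed shift (SHIM points) | SD 8.5 | SD 9.8 |
|---|---|---|
| 0 | 5.0% | 5.0% |
| 0.5 | 6.4% | 6.0% |
| 1 | 10.7% | 9.2% |
| 2 | 28.4% | 22.6% |

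As an example, for b = 1 at SD 8.5 the means are 1/1.437 = 0.696 (final) and 0.492 (interim).

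If there is a true benefit and the shift runs against the membrane, power falls. For that first row, a 1-point adverse shift leaves 2.80/1.352 = 2.071 (interim 1.464), and power drops from 80.1% to 54.2%.

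The calculation uses the unadjusted comparison and no futility stopping. The note to Table 10.1 prints 0.03 for the interim level where 10.7.3 has 0.003. That is a separate inconsistency and plays no part here.

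**The case against.** - **One loose word.** Section 10 shows other drafting residue, such as a reference to a sling and an unfilled placeholder in 10.7.2. The word blinded may be a leftover, and Section 4 never claims it. This is possible, and the documents do not settle it. If so, deleting the word cures the contradiction, and the timed release becomes an improvement to the design rather than the repair of an error.
- **Exposure is inferred.** This stands. A reader might infer that surgeons dissect knowing the arm, or that patients are told it. The documents say neither. The consent pages, which could state what patients are told, were not available. The plan permits early knowledge; it does not require it.
- **Existing safeguards.** Questionnaire data are de-identified and coded by participant number (7.4), and the packaging carries a stock number (5.2). The first protects data handling and the second identifies the product. Neither blinds the patient or the surgeon. Section 5.4 offers all men the same oral PDE5i programme and records use at each follow-up, and the 10.6 models adjust for oral aids. That limits one route of bias, but it cannot correct expectation in self-report or differences in dissection.
- **The percentages follow from the assumed shift.** This is so. They show sensitivity, and the textual point does not depend on them.

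**Conclusion.** The point holds in a limited form. The plan asserts blinding without naming a role, a method or an end date. Section 4.3 releases the arm with no hold until dissection is complete, although Sections 5.1 and 5.2 show that a hold would fit the order of the operation. The conclusion rests on the available sections only.

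It would go too far to say that the trial is in fact unblinded, that its result is biased, or that any bias favours the membrane. The documents give neither direction nor size. Across assumed shifts of 0.5 to 2 points and SDs of 8.5 to 9.8, the false-positive rate would run from 6.0% to 28.4% instead of 5.0%; a shift the other way would reduce power to detect a benefit. The change is worth making because the exposure is avoidable and the remedy is modest.

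**What to change.** - **Section 4.3:** release the assignment to the operating room only after nerve dissection is complete and the prostate is removed. Arrange membrane supply so that it does not reveal the arm beforehand.
- **Patients:** do not tell them the arm until the 12-month SHIM is complete. Keep the assignment form and the surgical notes, which 11.4 lists among the source documents, out of the papers used at questionnaire visits.
- **Questionnaires:** where possible, have any help given by existing staff who have not been told the arm.
- **Analysis:** keep every randomized man in the intention-to-treat analysis, as 5.7 already provides. This concerns analysis only and does not direct membrane placement.
- **Section 10:** state exactly who is blinded and until when, or delete the word if no one is.

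The cost is protocol wording plus a small release step in theatre. The sponsor must confirm that CIERRA and the coordinators can support it, because the documents do not show this. The surgeon and theatre staff will still know the arm after release, so the Section 10 statement should say so. Changing only the Section 10 wording costs one sentence, but leaves the possible exposure as it is.
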